Patients with implanted hypoglossal nerve stimulation (Inspire[®]) devices will be recruited for this protocol from the University of Pennsylvania or Thomas Jefferson University. All study procedures will be conducted by the clinical research team at the Hospital of the University of Pennsylvania campus (including HUP main, HUP Pavilion and PCAM). Medical records of these referrals will be assessed preemptively or at the time of the clinic or procedure visit for eligibility for this protocol. The patients will be asked whether they are interested in participating in the protocol, at which point informed consent will be obtained for those willing and eligible to enroll. Participants will also

complete a standard MRI screening form to assess eligibility for MRI, including potential claustrophobia.

Design (see Study Flow below)

Participants will initially be consented and screened for this study with a brief medical history and physical exam ([Visit #1](#)). The diagnosis of obstructive sleep apnea may be confirmed from prior sleep study reports. This visit may occur during routine clinical follow-up, if applicable, and may have already been completed prior to study enrollment (primary exception: Thomas Jefferson University patients). Once all inclusion criteria have been met, participants will continue with 3 additional assessments/visits (total 4 visits) per research protocol. In order to facilitate scheduling, these visits may occur in any order:

Eligible participants will undergo upper airway imaging ([Visit #2](#)), where craniofacial morphology will be assessed with MRI measurements and digital morphometric measurements (Study B only).

Participants will then attend an in-lab overnight sleep study ([Visit #3](#)). This will be a full standard polysomnography study where brain activity, body movements, modified EKG, respiratory parameters, and oxygenation will be monitored according to gold standard AASM guidelines. The sleep study will be performed in a split-night fashion including (1) a baseline sleep assessment to measure apnea severity, and (2) hypoglossal nerve stimulation with Inspire to measure response to therapy.

[figure not shown]

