1. **Baseline Questionnaires:** Standard screening questionnaires will be administered initially at the time subjects are screened and consented. These questionnaires will assess several demographic, anthropometric, and physical health domains (see attached questionnaires). We will administer the standard Sleep Surgery clinical questionnaire which includes ESS, ISI, FOSQ-10, NOSE, sleep quality, snoring, etc. We will perform an Inspire device download to evaluate study eligibility (therapy compliance), and record their treatment settings. Patients without the most recent Inspire remote will be provided with one.

Visit #2: Overnight Sleep Study, Digital Morphometrics, Tongue Force Assessment

1. **Sleep study monitoring (polysomnography):** Standard monitoring of sleep will occur during Visit #2. For patients opting for Study A only, the sleep study may have already been performed as part of routine clinical care. For Study B, overnight nocturnal recordings will be performed in our sleep laboratory and will follow the same procedures (#1-5) outlined in Visits #3-4 below. The study will include monitoring of EEG, submental EMG, EOG, S_pO_2 , tidal airflow, thoraco-abdominal efforts, and body position. Recordings will be archived on an institutionally secured and managed network drive and accessible only to study personnel. Recordings will be accessed via a HIPAA secured web portal. Patients will be required to wash out from therapy between 5-7 days prior to PSG, i.e. they cannot use HGNS or other therapies during this time. A split night study will be performed (partially with HGNS, partially without). HGNS will not be titrated, i.e. we will use the settings optimized by clinical care prior to study participation. Patients must have a minimum of one hour of supine non-REM stage 2 sleep during both the baseline and treatment (with HGNS) assessments. If patients are unable to meet these criteria, they will not proceed with DISE.

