2. **CPAP Level Manipulation:** The nasal pressure will be manipulated to measure pharyngeal cross-sectional area and tidal airflow at various levels of upper airway patency, as previously described⁴⁶⁻⁶⁸. Nasal pressure will be maintained at an elevated holding pressure at which airflow obstruction is abolished, and then dropped step-wise for several breaths to pressures that induce inspiratory flow limitation and complete obstruction.
3. **Pharyngeal Manometry:** In addition to standard sleep monitoring, up to two 7 French Millar catheters (Houston, TX) will be passed perinasally to monitor pharyngeal pressure swings and will be used subsequently as an internal calibration marker for measurements of pharyngeal cross-sectional area on videoendoscopy images during sleep studies^{32,33}. To facilitate this process, we will administer 2% Viscous Lidocaine perinasally before passing the catheter(s).
4. **Ultrasound procedures:** Ultrasound will be performed in each study participant after propofol-induced sleep has been initiated. Measurements during DISE will take about 10 minutes. Images will be acquired with and without stimulation of tongue protrudors.

5. **Lingual Muscle Stimulation (Study B only):**

Patients will have already undergone HGNS implantation and device setting optimization as part of clinical standard-of-care. The Inspire programmer will be used to turn on and off stimulation during DISE and PSG procedures.

b. Study duration and number of study visits required of research participants.

Each participant will be asked to participate for the duration of Visit 1 (1-2 hour clinic visit), Visit 2 (up to one half day for imaging procedures), Visit 3 (baseline overnight sleep study), and Visit 4 (1 half day for DISE procedure). We anticipate that approximately 20% of participants will not be able to complete all of these visits. Participants' participation in these assessments will remain completely voluntary.

We estimate that it will take us about 5 years to collect, process, and fully analyze the ultrasound and DISE study data. Each subject's active participation is anticipated to last for about 1 month.

c. Blinding, including justification for blinding or not blinding the trial, if applicable.

There is no blinding of subjects. Investigators will be blinded before measurement of acquired images to avoid observer confirmation bias.

d. Justification of why participants will not receive routine care or will have current therapy stopped.

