Participants will temporarily stop all therapy for OSA (particularly Inspire) for 5-7 nights prior to their sleep study. Each participant's medical therapy will continue unaffected by this study with the addition of submental ultrasound examination, MRI, and of one unscheduled polysomnography.

5. Inclusion/Exclusion Criteria

Inclusion Criteria:

- Adult patients (≥ 22 yrs) willing and capable of providing informed consent
- Implanted with the MRI-conditional Inspire hypoglossal nerve stimulator (Model 3028)*
- Compliant with Inspire therapy (> 20 hours/week over 2+ weeks) as a standalone treatment for sleep-disordered breathing
- Inspire Remote Model 2500 or later

Exclusion Criteria:

- MRI contraindications (claustrophobia, ferromagnetic implants/foreign bodies, etc.)*
- Inspire Model 3024
- Inspire Remote Model 3032
- Patients who have fallen asleep while during resulting in an accident or “near miss” accident within 1 year prior to device implantation.
- Inability to sleep in the supine position (by self report)
- History of severe difficulty initiating or maintaining sleep in the laboratory.
- Pregnant women**

* The Inspire model 3028 is not considered an MRI contraindication.

**Women of child bearing potential must undergo a urine pregnancy test (UPT) prior to enrollment. A second UPT is performed prior to DISE as part of routine clinical workup. This study involves temporarily stopping treatment of obstructive sleep apnea, which may harm the fetus.

6. Drugs/Substances/Devices

a. The rationale for choosing the drug and dose or for choosing the device to be used.

We will administer propofol, which is routinely given for DISE procedures. The rationale for choosing this drug is based on its reliability, well-established tolerability, safety, and low muscle-relaxant profile.

Lidocaine jelly (~ 2 mL) will be squirted into each nostril prior to passing the pharyngeal catheter and endoscope.

The protocol will involve recruiting patients already implanted with the Inspire HGNS system. We have selected this device in place of stimulating with custom fine-wire electrodes to reduce patient burden. The Inspire device is safe, well-tolerated, and FDA-approved for treatment for OSA.

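### The pregnancy tests are tied to enrolment and DISE, but the therapy stop that the plan names as the fetal hazard is tied to the sleep study

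*SAP*

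**What the plan says.** The same footnote to the eligibility criteria appears in the Study Summary and in section 5. It makes three statements:

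- First test: "Women of child bearing potential must undergo a urine pregnancy test (UPT) prior to enrollment".
- Second test: "A second UPT is performed prior to DISE as part of routine clinical workup".
- Reason: "This study involves temporarily stopping treatment of obstructive sleep apnea, which may harm the fetus".

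The therapy stop is timed to the sleep study. Section 4d says "Participants will temporarily stop all therapy for OSA (particularly Inspire) for 5-7 nights prior to their sleep study". The sleep-study procedures in section 4a say "Patients will be required to wash out from therapy between 5-7 days prior to PSG". Section 7d and the Therapy Washout paragraph of section 8a also describe a 5-7 night washout, with a check-in call after two nights.

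Four other statements bear on the order of events:

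- Section 4a says of the imaging, sleep study and DISE visits: "In order to facilitate scheduling, these visits may occur in any order".
- The sleep-study procedures in section 4a require at least an hour of supine stage 2 non-REM sleep both with and without stimulation. Patients who fall short do not go on to DISE.
- The footnote under the visit table in section 4a lets screening and consent take place at whichever assessment comes first, including the PSG.
- Section 4b says that each subject's "active participation is anticipated to last for about 1 month".

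**The concern.** An eligibility check protects against a hazard only if it still holds when the hazard begins. The footnote names a single hazard, the interruption of OSA treatment. That interruption is set by the PSG date, while the tests are set by enrolment and by the DISE date. Nothing in the document links either test to the start of the washout or limits how old the enrolment test may be at that point.

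Participant safety is at stake. A site could follow the plan exactly, and a woman who became pregnant after enrolment could still stop therapy. Her pregnancy would then be found after the exposure, or not at all within the study. The one contact described during the washout, the check-in call, does not close the gap: the only question specified for it (section 7d) is about falling asleep while driving.

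**Working it through.** The plan states no figure to reproduce here. The check sets the timing statements side by side and adds calendar arithmetic.

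**Where each event is anchored**

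| Event | Anchor | Source in SAP |
|---|---|---|
| First urine test | Before enrolment, no window | Study Summary; section 5 |
| Second urine test | Before DISE | Study Summary; section 5 |
| Start of therapy stop | 5-7 nights before the PSG | Sections 4a, 4d |
| Order of MRI, PSG, DISE | Free | Section 4a, design text |
| DISE conditional on PSG | PSG sleep requirement must be met | Section 4a, sleep-study procedures |
| Consent | May coincide with the first assessment | Section 4a, visit table footnote |

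**What each order implies**

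1. *PSG before DISE.* The PSG sleep requirement implies this order. The washout ends at the PSG and the second test is tied to the later DISE, so that test can come after the exposure. A woman who misses the sleep requirement never reaches it.
2. *DISE before PSG.* The free visit order allows this. The pre-DISE test may then be the most recent one before the washout, but no interval connects the two. This order also conflicts with making DISE conditional on the PSG.
3. *Consent at the PSG visit.* The visit table footnote allows this. Read literally, the 5-7 nights off therapy have already passed when the woman consents, so the washout can precede even the enrolment test.

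**Age of the enrolment test when therapy stops**

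Let P be the day of the PSG counted from an enrolment-day test, and W the washout length (5 to 7 days).

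Age of test at start of washout = P − W.

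- Longest: assume 1 month = 30 days and the PSG at the very end, P = 30. Then 30 − 7 = 23 and 30 − 5 = 25 days.
- Shortest with the test before the washout: therapy stops on the day of enrolment, P = W, which gives 0 days.
- Consent and test at the PSG visit: P = 0. Then 0 − 7 = −7 and 0 − 5 = −5, so therapy stopped 5 to 7 days before the test.

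When the test comes first, the range is therefore about 0 to 25 days.

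**How firm the upper end is**

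- If the PSG is last, DISE has already taken place. With DISE and its test on day d, before the washout starts, the latest test is 23 − d to 25 − d days old. The figure of 23 to 25 days ignores that test.
- If the PSG comes first and DISE follows at least a day later within the same 30 days, P is at most 29. The longest gap is then 29 − 7 = 22 to 29 − 5 = 24 days, with no intervening test.
- The month is only anticipated and the first test has no window before enrolment, so 25 days is not a strict ceiling.

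**The case against.** The strongest reply is that the footnote does not contradict itself. The stated reason supports the exclusion and does not set a test schedule. The first test checks eligibility at entry, where an exclusion is normally checked. The second is described as routine DISE work-up and is never offered as protection during the washout. This stands in part. It would be wrong to call the pre-DISE test a failed washout safeguard, because the plan gives it no such purpose. But it follows that the only study-specific test is the one at enrolment, and nothing keeps that test current until therapy stops.

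A second reply is that a test window is a detail an SAP may leave to a protocol. That would hold for a bare omission. Here the same document sets the eligibility criteria, tests, washout, visit order and consent timing, and the mismatch lies among those statements.

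A third reply is that the long gap is a corner case. That stands. A reader might infer that women will routinely stop therapy on a test more than three weeks old. The documents do not support this: the gap can be close to zero, and the figure of 23 to 25 days needs the PSG at the end of the month and disregards any earlier pre-DISE test.

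A reader might also infer from the visit table footnote that the plan intends therapy to stop before consent. The text does not support that either. Section 4a has participants go on to the assessments once the inclusion criteria are met, and section 8a places the advice about driving while sleepy at consent. The footnote permits a sequence that these statements do not envisage, so it is one more item to reconcile.

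**Conclusion.** The concern holds as a misplaced safeguard of minor severity. The tests follow enrolment and DISE, the named hazard follows the PSG, and none of the permitted sequences requires a test to be current when therapy stops.

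The enrolment test may be about 0 to 25 days old at that point. This assumes 30 days of participation, a test on the day of enrolment and a 5-7 day washout. If consent is taken at the PSG visit, the test may come after the washout.

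A stale test is a possibility under the plan, not a certainty. The documents do not give the number of women of child-bearing potential; that it is small is an assumption. Sample size and analysis are unaffected.

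**What to change.** Reconcile the pregnancy-test timing in the Study Summary and section 5 footnotes with:

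- the washout timing in sections 4a, 4d, 7d and 8a;
- the free visit order in section 4a;
- the rule in section 4a that makes DISE conditional on the PSG;
- the visit table footnote that lets consent coincide with the first assessment.

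The reconciled text should make clear how the safeguard covers the hazard that the footnote names, whichever visit order is used. Which clinical rule achieves this is for the sponsor and the IRB to decide.

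The direct cost is a wording amendment to a few sections. Whether any testing is added or re-timed depends on their decision.

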Using an ANOVA framework for estimating sample size for a 1x3 factorial design (Specific Aim A: complete responder, partial responder, and non-responder), we calculate the sample required to detect within-subject changes in upper airway function (e.g., the severity of upper airway obstruction during DISE as reflected by measurements of pharyngeal collapsibility, P_{CRIT}), based on published data demonstrating decreases in pharyngeal collapsibility (P_{CRIT}) of $\sim 3.5 \pm 2.0$ cmH₂O during stimulation ³⁴. This response accounts for $\sim 24\%$ of the total variance (η^2), which yields an effect size (f) of ~ 0.40 . Our data also demonstrate within-subject correlations of at least 0.5 for repeated P_{CRIT} measurements ^{69,70}. Using these parameters, we calculated that 15 subjects would be required to detect significant differences in each of 3 responder categories with an alpha of 0.05 and a power of 90%. To account for measurements in both sexes, subject attrition, and incomplete measurements, we propose an 'n' of 45 subjects to complete the protocol. We also plan to examine the effects of sex and BMI on this outcome, which will require an additional 30-60 subjects (total n = 100) for the entire protocol. This sample size will allow us sufficient power to detect substantial effects of stimulation on tongue morphology (Specific Aim B) and effects of craniofacial structures on tidal airflow and markers of airway collapsibility (Specific Aim C).

d. Early stopping rules.

- This is a low-risk study designed to examine underlying mechanisms of action of lingual and hypoglossal nerve stimulation treatment in patients with obstructive sleep apnea. Since the protocol will involve temporarily stopping HGNS treatment for 5 days, one risk includes excessive daytime sleepiness. We have attempted to minimize subject risk with the strict exclusion criterion, "Patients who have fallen asleep while during resulting in an accident or 'near miss' accident within 1 year prior to device implantation." In addition, we will advise patients against driving and operating heavy machinery during this 5-7 night washout period and we will perform a check-in call after the first 2 nights without therapy. We will specifically ask patients if they have fallen asleep while driving, and will withdraw any patients answering yes. We also recognize and inform each subject of his/her right to withdraw from the clinical study at any time.

8. Risks

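### Aim A is sized on three undefined responder categories; if these are cut from the split-night response, using it continuously would avoid losing up to about 22–23 points of power (equal categories)

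*SAP*

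**What the plan says.** Section 7c sizes the study in an ANOVA framework with one three-level factor: "Specific Aim A: complete responder, partial responder, and non-responder". Within that framework, "we calculate the sample required to detect within-subject changes in upper airway function", with P_CRIT as the example. The inputs are a share of variance of about 24%, "which yields an effect size (f) of ~ 0.40", a within-subject correlation of at least 0.5, and the test is run "with an alpha of 0.05 and a power of 90" percent. The result is 15 subjects for the three categories, 45 to complete the protocol and 100 in total. Section 4b expects about 20% of participants not to complete all visits.

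The three categories appear only in that paragraph. The SAP states no cut-points, no source variable and no analysis of response as a continuous quantity.

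Section 4a describes a split-night study with a baseline part for apnea severity and a part using "hypoglossal nerve stimulation with Inspire to measure response to therapy". The sleep-study item in the same section adds: "Patients must have a minimum of one hour of supine non-REM stage 2 sleep during both the baseline and treatment (with HGNS) assessments". A patient who does not meet this does not go on to DISE. Section 8a names the AHI in episodes per hour, but only as a notification threshold.

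The opening of section 7 makes stimulation on or off the primary independent variable, with tongue and craniofacial measurements as further predictors.

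**The concern.** Every Study B participant who reaches DISE should have sleep recordings both off and on stimulation, so an event rate can be calculated for each part. Cutting such a measure into three classes discards the differences inside each class. It spends two degrees of freedom instead of one, and it lets noise in a part-night recording move patients near a cut-point from one class to another. What is at stake is the comparison that section 7c sizes: whether the mechanical effect of stimulation (P_CRIT change at DISE) differs by response to therapy. A true link would be missed more often than it need be.

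Because the source variable is not named, there is a second risk. If response were classified from the DISE measurements themselves, comparing P_CRIT change across the classes would be circular.

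**Working it through.** **1. The plan's own figure.** The two stated effect measures do not agree: η² = 0.24 gives f = √(0.24/0.76) = 0.562, while f = 0.40 gives η² = 0.16/1.16 = 0.138. The figure 15 can be reached in two ways:
- One-way ANOVA, three groups, f = 0.562, 15 per group: λ = 45 × 0.24/0.76 = 14.2, power 91.3%.
- One group measured three times, f = 0.40, ρ = 0.5, 15 subjects in all: λ = 0.16 × 15 × 3/(1 − 0.5) = 14.4, power 90.6%.

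A one-way ANOVA with f = 0.40 gives 63.5% at 45 and needs 84 in total. The mismatch is a separate matter, so both effect sizes are carried forward.

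**2. Inputs for the loss.** From the SAP: 45 subjects; 100 × (1 − 0.20) = 80 completers; α = 0.05; f = 0.40 or η² = 0.24. An equal split is implied by 45 = 3 × 15. Assumed: response X and P_CRIT change Y are approximately bivariate normal with correlation r, and the categories are cut from X.

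**3. Formulas.** The share of the variance of X kept by three groups with proportions c is e = Σ(φ(lower cut) − φ(upper cut))²/c, where φ is the standard normal density. Equal thirds keep e = 0.793; 70/20/10 keeps 0.63.
- Continuous: F test on 1 and N − 2 df, λ = N·r²/(1 − r²).
- Grouped: F test on 2 and N − 3 df, λ = N·e·r²/(1 − e·r²).

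The stated effect may be what the groups explain (r² = η²/e) or what the continuous response explains (r² = η²), so both readings are shown.

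**4. Equal categories, power in %.**

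| N | Stated effect, taken as | λ continuous / grouped | Continuous | Grouped | Loss |
|---|---|---|---|---|---|
| 45 | f 0.40, grouped | 9.5 / 7.2 | 85.3 | 63.5 | 21.8 |
| 45 | f 0.40, continuous | 7.2 / 5.5 | 74.6 | 51.6 | 23.0 |
| 45 | η² 0.24, grouped | 19.5 / 14.2 | 99.1 | 91.3 | 7.8 |
| 45 | η² 0.24, continuous | 14.2 / 10.6 | 95.8 | 80.9 | 14.9 |
| 80 | f 0.40, grouped | 16.8 / 12.8 | 98.2 | 89.1 | 9.1 |
| 80 | f 0.40, continuous | 12.8 / 9.8 | 94.2 | 79.2 | 15.0 |
| 80 | η² 0.24, grouped | 34.7 / 25.3 | 100.0 | 99.6 | 0.4 |
| 80 | η² 0.24, continuous | 25.3 / 18.8 | 99.9 | 97.5 | 2.4 |

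Over all values of r, the largest loss is about 23 points at 45 and about 22 at 80 and at 100. Simulation of the same model (8,000 to 20,000 replicates) gives powers up to about 2.5 points lower and losses within about 1 point of these.

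**5. Unequal categories (the split and the correlations are assumptions).**
- N = 80, r = 0.35: continuous 91.0%, thirds 73.3%, 70/20/10 61.5%. The losses are 17.7 and 29.5 points.
- N = 45, r = 0.40: continuous 81.6%, thirds 59.1%, 70/20/10 47.7%. The losses are 22.5 and 33.9 points.
- With one third in the lowest class and a 33/17/50 split, the largest loss is about 28 points at 45 and 25–26 at 100.

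**6. The on/off contrast.** This does not use the categories. If 3.5 ± 2.0 cmH₂O is read as a paired change with SD 2.0 (an assumption), the standardized change is 3.5/2.0 = 1.75 and about 6 subjects suffice.

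**The case against.** **The categories may be only a sizing device.** They appear once, inside a sample size calculation. Section 7 names on/off stimulation as the primary independent variable and does not list responder class as a predictor. The Study B objectives in section 2 concern the effect of stimulation and prediction by craniofacial morphology, not P_CRIT change against sleep-study response. This stands as a limit on the point: the primary contrast loses nothing. It does not remove the point, because section 7c sizes Aim A for differences among the three classes, and that comparison bears the loss.

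**The source is inferred.** Nothing says that the classes come from the split-night study. That study is the one assigned to measure response to therapy, so the inference is reasonable, but the loss remains conditional on it.

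**A reader might infer that the plan gives up about 30 points of power at its planned size.** The documents do not support this. Fifteen per class is an equal split, for which the ceiling is about 22–23 points. The only figure on response, the background statement in the abstract that about one third of patients did not respond, does not point to a 10% class. A compliant sample at optimized settings might well split unequally, and nothing in the plan fills the classes evenly, but no split is stated.

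**The comparison favours the continuous analysis.** Linearity and normality are assumed, and part-night noise also attenuates a slope. A plain log ratio is undefined when the treated event rate is zero. These points are fair and shape the fix.

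**Conclusion.** The point holds as one of efficiency and specification. Section 7c sizes Aim A on three responder classes without cut-points or a source variable, while a continuous response appears to be available in every participant who reaches DISE. If the classes are cut from that response and are equal in size, the cost to the responder comparison is at most about 22–23 points of power. At the plan's own effect sizes it is about 8–23 points at 45 subjects and 0–15 at 80 completers; at 100 it is 10 points or less. A loss of about 30 points or slightly more needs a clearly unequal split, which is an assumption and not a property of the plan. These figures rest on approximate bivariate normality, a linear relation and the inferred source of the classes. The on/off stimulation effect is unaffected.

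**What to change.** In section 7c, define response for the Aim A responder comparison as a continuous quantity from the split-night study, and enter it as a linear moderator of the stimulation effect on P_CRIT. Two workable forms are:
- the on-stimulation event rate, adjusted for the off-stimulation rate; or
- the log ratio of the on rate to the off rate, with a small prespecified constant added to both so that zero rates are defined.

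With one on and one off P_CRIT value per subject, this amounts to regressing the P_CRIT change on response. State that response is not derived from the DISE measurements. Define the three classes with their cut-points and report P_CRIT change by class descriptively.

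The cost is SAP wording, with no further visits, patients or measurements. The downsides are that linearity is assumed and should be checked (for example with a plot and a curvature term), and that the result is a slope instead of a clinically familiar contrast between classes; the descriptive table partly makes up for this.

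### The sample-size chain in SAP section 7c (3.5 ± 2.0 cmH2O, 24% of variance, f 0.40, correlation 0.5, 15 subjects) does not hold together under any one reading of 2.0 or any one correlation

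*SAP*

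**What the plan says.** SAP section 7c sets the calculation out as one chain.

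- The design is a "1x3 factorial design (Specific Aim A: complete responder, partial responder, and non-responder" comparison, described as detecting within-subject change in upper airway function, with PCRIT as the example.
- The size of the effect is "based on published data demonstrating decreases in pharyngeal collapsibility", namely about 3.5 ± 2.0 cmH2O during stimulation, cited to a genioglossus stimulation study (reference 34).
- This response is said to account for about 24% of total variance, "which yields an effect size (f) of ~ 0.40".
- The plan then adds "within-subject correlations of at least 0.5 for repeated" PCRIT measurements, cited to a palatal surgery study and a weight-loss study (references 69 and 70).
- From these it obtains 15 subjects in each of three responder categories, "with an alpha of 0.05 and a power of 90" percent. It then proposes 45 to complete the protocol and 100 in all.

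The section does not say whether 2.0 is an SD of the change, an SD within each state or a standard error. It does not say what the total variance contains, or how 24% was obtained. Section 7 opens by naming stimulation on versus off as the primary independent variable.

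**The concern.** A reader should be able to go from the cited change to the variance share, from there to f, and from f and the correlation to n. Here the steps do not meet. The cited change looks much larger than the f that is used, and the correlation needed to shrink it to 24% or to f 0.40 is not the one at which f 0.40 gives 15.

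At stake is whether 15, and the 45 and 100 built around it, can be said to follow from published data. If f 0.40 was a deliberately smaller effect, that is legitimate, but the plan should say so. If it is a slip, the figures should be corrected.

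**Working it through.** **Inputs (all SAP 7c):** change 3.5; spread 2.0 (undefined); η² 0.24; f 0.40; correlation ρ at least 0.5; alpha 0.05; power 90%; three responder categories.

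**Formulas.** For an on/off change δ with within-state SD σ: f = (δ/2)/σ and η² = f²/(1+f²). The SD of the change is σ·√(2(1−ρ)). For a repeated-measures within factor with m levels and N subjects, the noncentrality is λ = f²·N·m/(1−ρ). For a one-way design, λ = f²·N.

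**1. Reproducing 15.** Two routes give it.
- f 0.40, ρ 0.5, one group, three repeated levels: N = 15 in total, power 0.906.
- η² 0.24 (so f 0.562), one-way ANOVA of three groups: N = 45, or 15 per category, power 0.913. This route uses neither f 0.40 nor the correlation.

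Other designs at f 0.40 (ρ 0.5 where a correlation enters) need totals of 19 (on/off, one group), 21 (on/off, three groups), 24 (on/off by category interaction), 63 (between categories, two measures) and 84 (one-way).

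**2. η² to f, which needs no reading of 2.0.** √(0.24/0.76) = 0.562. Conversely, 0.40²/(1+0.40²) = 0.138. So 24% and f 0.40 are not the same effect.

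**3. 2.0 as the SD within each state.** f = 1.75/2.0 = 0.875; η² = 0.766/1.766 = 0.434. The correlation does not enter.

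**4. 2.0 as the SD of the change.** σ = 2.0/√(2(1−ρ)), so the answer depends on ρ:

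| ρ | σ | f | η² |
|---|---|---|---|
| 0.5 | 2.00 | 0.875 | 0.434 |
| 0.7 | 2.58 | 0.678 | 0.315 |
| 0.794 | 3.12 | 0.562 | 0.240 |
| 0.85 | 3.65 | 0.479 | 0.187 |
| 0.896 | 4.375 | 0.40 | 0.138 |

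Thus 24% needs ρ of about 0.79, and f 0.40 needs about 0.90.

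**5. Carrying one ρ through to n.** Under the SD-of-change reading, f²/(1−ρ) = (3.5/2.0)²/2 = 1.53 whatever ρ is. The inputs that reproduce 15 give 0.40²/0.5 = 0.32. Setting dz²/2 = 0.32 gives dz = 0.80, that is an SD of change of 3.5/0.80 = 4.4, not 2.0. With 1.53, the three-level design needs 5 subjects (power 0.947) at any ρ.

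**6. 2.0 as a standard error (an assumption; the source sample size is not given).** At ρ 0.5 the SD of change is 2.0·√n. For 24%, n = (3.11/2.0)² = 2.4. For f 0.40, n = (4.375/2.0)² = 4.8. A source of n = 5 gives η² 0.133, and n = 10 gives 0.071.

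**7. Another denominator.** The 43% already includes between-subject variance. Removing it gives 1.75²/(1+1.75²) = 0.75, which is further from 24%.

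**The case against.** The strongest defence is that the derivation is undocumented rather than shown to be wrong. The correlation is a floor, not a value. It comes from different studies than the change does, and it is introduced after η² and f. The 24% may have been computed from the stimulation study's own total variance, with 0.5 then used as a cautious value for power. Much of this stands. A reader might infer that 3.5 ± 2.0 cannot give 24%; the document does not support that. If 2.0 is the SD of the change, ρ of about 0.79 gives 24%, and the plan's wording allows it. The 43% is the upper end under that reading, and a standard-error reading falls well below it.

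The defence does not repair the chain. At ρ 0.79 the f is 0.56, not 0.40, and f 0.40 needs a different ρ. The one-way route does give 15 per category from 24%. But it leaves f 0.40 and the correlation unused, and it treats an on/off change as a difference between responder categories, for which section 7c gives no data.

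A second tempting inference is that 6 subjects would do instead of 15. Six is right for a single paired on/off contrast at dz 1.75 (power 0.923), but the plan states its 15 for each of three responder categories, so the two figures answer different questions.

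Third, a reader might infer an underpowered study. The direction is the opposite: at f 0.875 and ρ 0.5 the total is 5 (three repeated levels), 6 (on/off paired), 9 (interaction) or 21 (one-way), all below 45.

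**Conclusion.** The point holds as an internal inconsistency. The 24%, the f of 0.40, the correlation and the 15 cannot all come from 3.5 ± 2.0 under one definition of 2.0 and one correlation. Its size: f 0.40 against 0.875 if 2.0 is an SD and ρ is 0.5; or an implied SD of change of 4.4 against the 2.0 cited, if 2.0 is the SD of the change. The mismatch between 24% (f 0.56) and f 0.40 (about 14%) rests on no assumption. The remaining figures depend on what 2.0 is and, for the SD-of-change reading, on ρ.

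It would go too far to say that the calculation has no basis in the cited data, since the document does not show how 24% was reached. Nor does the discrepancy show that the on/off contrast lacks power. It is worth correcting because the sample size is presented as following from these figures.

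**What to change.** In section 7c:

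- State whether 2.0 is the SD of the change, the SD within each state or a standard error (with the source sample size).
- Recompute η² and f from it with one stated correlation, and replace 24% and 0.40 with the consistent pair. Alternatively, say that a smaller effect than the published one was chosen as conservative, and give it.
- Restate n for the design that will be tested (on/off within subject, responder categories between subjects, or their interaction), and say whether it is a total or per category.

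This costs one paragraph; enrolment need not change.

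An optional addition, which does not follow from the discrepancy: section 7c also claims adequate power for craniofacial predictors without giving a detectable effect. By Fisher's z at 90% power and two-sided 0.05, r = tanh(3.24/√(n−3)). This is about 0.35 with 80 completers (100 less the roughly 20% that section 4b expects not to complete all visits) and 0.32 with 100. One sentence would support the claim.
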